# 6.3.3.4.3 Analysis

The change from baseline to Week 1–Week 4 for PGA-S (daytime symptoms) and the change from baseline to Week 4 for PGA-S (daily life) will be summarized by treatment. Observed values will also be summarized.

# 6.3.3.4.4 PGI-C endpoints

The PGI-C (daytime symptoms) is indicative of the change in overall severity of daytime symptoms (e.g., sleepiness) and impact (e.g., effort to perform daily activities) that the subject may have experienced due to their *insomnia* over the 7 days preceding the PGI-C (daytime symptoms) compared to the week before he/she started treatment. The PGI-C (daytime symptoms) is a 1-item, 7-point scale that ranges from 'Very much better' to 'Very much worse'. It will be completed weekly by the subjects on the eDiary during both treatment periods.

The PGI-C (nighttime symptoms) is indicative of the change in the subject's insomnia symptoms at night (e.g., trouble falling asleep, total time asleep, time to fall back asleep or number of times they wake up) over the 7 nights preceding the PGI-C (nighttime symptoms) compared to the week before the subject started treatment. The PGI-C (nighttime symptoms) is a 1-item, 7-point scale that ranges from 'Very much better' to

'Very much worse'. It will be completed weekly by the subjects on the eDiary during both treatment periods.

The PGI-C (daily life) is indicative of the change in overall severity of daily life symptoms that the subject may have experienced due to their *insomnia and nocturia* over a period of 4 weeks. The PGI-C (daily life) is a 1-item, 5-point scale that ranges from 'Very much better' to 'Very much worse'. It will be completed by the subjects on the eDiary at Visit 4 and Visit 8.

#### 6.3.3.4.5 *Variable*

The PGI-C (daytime symptoms) scale ranges from 1–7, the PGI-C (nighttime symptoms) ranges from 1–7, and the PGI-C (daily life) ranges from 1–5.

The same time window approach will be used for PGI-C (daytime symptoms) data as described in Section 6.3.3.4.2.

# 6.3.3.4.6 Analysis

The two PGI-C symptom scores will be summarized by week (Week 1, Week 2, Week 3, and Week 4). The PGI-C (daily life) score will be summarized for Week 4.

# 6.3.3.5 IDSIQ endpoints

IDSIQ is programmed on the eDiary and must be completed by the subject every day in the evening prior to completing the evening sleep diary. IDSIQ is structured in 3 domains (alert/cognition; mood; sleepiness) and contains 14 items overall, each based on an 11-point Numeric Rating Scale.

#### 6.3.3.5.1 *Variable*

The different IDSIQ domains are derived as shown in Table 5.

Table 5 Insomnia Daytime Symptoms and Impacts Questionnaire description

Domain	Scoring	Minimum/Maximum Score
	Daily: Sum of Item 1*, Item 2*, Item 3, Item 9, Item 10*, Item 14*	Minimum score: 0 Maximum score: 60
Alert/Cognition	Weekly Average: Mean of the daily domain score over 7 days	Higher score: greater burden of illness
Mood	Daily: Sum of Item 4, Item 5, Item 6, Item 7 Weekly Average: Mean of the daily domain score over 7 days	Minimum score: 0 Maximum score: 40 Higher score: greater burden of illness

Page 33/50

Statistical Analysis Plan for Clinical Study Report Version 2 Doc No D-24.149

Domain	Scoring	Minimum/Maximum Score
Sleepiness	Daily: Sum of Item 8*, Item 11, Item 12, Item 13	Minimum score: 0 Maximum score: 40 Higher score: greater burden of illness
	Weekly Average: Mean of the daily domain score over 7 days	
Total score	Daily: Sum of all domains above  Weekly Average: Mean of the daily domain score over 7 days	Minimum score: 0 Maximum score: 140 Higher score: greater burden of illness

\* Item 1, Item 2, Item 8, Item 10, and Item 14 scores are reverse-scored prior to summation.

Baseline is the mean value based on the IDSIQ entries performed at home on the 7 days immediately preceding Visit 2.

Week 1—Week 4 are defined as the mean values based on the IDSIQ entries performed during Days 2–8, 9–15, 16–22 and 23–29 in each treatment period, respectively. In order to calculate baseline and Week 1–Week 4 averages, at least two days of data must be available. Otherwise, baseline and weekly averages are considered as missing.

### 6.3.3.5.2 *Analysis*

For all IDSIQ scores, weekly averages and corresponding changes from baseline to Week 1–Week 4 will be summarized, by treatment. Changes from baseline to Week 1–Week 4 will also be analyzed for all IDSIQ scores based on an MMRM, as described in Section 6.1.3.

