1 PROTOCOL SUMMARY

1.1 Protocol synopsis ID-078A401

TITLE	A multi-center, double-blind, randomized, placebo- controlled, 2-way cross-over post approval study to investigate the efficacy of daridorexant in subjects with insomnia and comorbid nocturia
OBJECTIVES	Efficacy objectives
	The primary objective of this study is to assess the efficacy of daridorexant on insomnia in subjects with insomnia and comorbid nocturia. The following variables will be evaluated:
	a) Quantitative measure of subjective total sleep time (sTST) by the Sleep Diary Questionnaire (SDQ).
	b) Overall rating of the insomnia severity by the Insomnia Severity Index [©] (ISI [©]).
	c) Other SDQ-derived variables: (i) quality of sleep visual analog scale (VAS), (ii) depth of sleep VAS, (iii) daytime alertness VAS, (iv) daily ability to function VAS, and (v) number of awakenings.
	The secondary objective is to assess the efficacy of daridorexant on nocturia. There is no data for daridorexant in subjects with insomnia and comorbid nocturia. The following variables will be evaluated:
	a) Voiding diary-derived assessments: (i) time to the first nocturnal void, (ii) each voiding volume (nighttime and daytime) including total volume, (iii) number of nocturnal voids.
	b) Lower urinary tract symptoms (LUTS) sub-score using the International Consultation on Incontinence Questionnaire (ICIQ) -MLUTS and -FLUTS for male and female subjects, respectively.
	c) Quality of life relative to nocturia, assessed by ICIQ Nocturia Quality of Life (ICIQ-NQoL).

version 5	
4 September 2023, page 17/122	

	Other objectives will focus on subject's overall assessment ratings of their condition and symptoms including:
	a) Patient Global Assessment of Disease Severity and Patient Global Impression of Change for insomnia and for nocturia.
	b) Quality of life using the European Quality of Life 5 Dimensions 3 Level Version (EQ-5D-3L).
	c) Overall assessment of subjective treatment satisfaction by numeric rating scale.
	d) Subject preference for treatment.
	In addition to efficacy and safety, the following exploratory efficacy endpoints will be studied:
	a) The sensitivity of the Insomnia Daytime Symptoms and Impacts Questionnaire to detect clinical changes in this study population,
	b) The use of narratives to report subject's perception of treatment effect.
	Safety objectives
	The safety objectives will be to assess the safety and tolerability of daridorexant based on:
	a) Adverse event (AE) reporting

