3 STUDY OBJECTIVES AND ENDPOINTS

3.1 Objectives

The overall objective of this study is to explore the clinical efficacy of daridorexant and to further evaluate its safety and tolerability in subjects with insomnia and comorbid nocturia.

Based on the mode of action of daridorexant and the knowledge acquired during its development, it is reasonable to identify the following objectives to be explored in this study:

Efficacy objectives

The primary objective of this study is to assess the efficacy of daridorexant on insomnia in subjects with insomnia and comorbid nocturia. The following variables will be evaluated:

- a) Quantitative measure of sTST by the SDQ.
- b) Overall rating of the insomnia severity by the ISI[©] with a recall period of 2 weeks.
- c) Other SDQ-derived variables: (i) quality of sleep VAS, (ii) depth of sleep VAS, (iii) daytime alertness VAS, (iv) daily ability to function VAS, and (v) number of awakenings.

The secondary objective is to assess the efficacy of daridorexant on nocturia. There is no data for daridorexant in subjects with insomnia and comorbid nocturia. The following variables will be evaluated:

a) Voiding diary derived assessments: (i) time to the first nocturnal void, (ii) each voiding volume (nighttime and daytime) including total volume, (iii) number of nocturnal voids.

4 September 2023, page 36/122

- b) Lower urinary tract symptoms sub-score using the ICIQ-MLUTS and -FLUTS for male and female subjects, respectively.
- c) Quality of life relative to nocturia assessed by ICIQ-NQoL.

Other objectives will focus on patient's overall assessment ratings of their condition and symptoms including:

- a) PGA-S and PGI-C for insomnia and for nocturia.
- b) Quality of life using the EQ-5D-3L.
- c) Overall assessment of subjective treatment satisfaction by NRS.
- d) Subject preference for treatment.

In addition to efficacy and safety this study the following exploratory efficacy endpoints will be studied a) the sensitivity of the IDSIQ to detect clinical changes in this study population, and b) the use of narratives to report subject's perception of treatment effect.

Safety objectives

The safety objectives will be to assess the safety and tolerability of daridorexant based on:

- a) AE reporting.
- b) Occurrence of suicidal ideation, suicidal behavior and/or self-injurious behavior with/without suicidal intent based on the C-SSRS[©].
- c) Morning sleepiness as determined by morning sleepiness VAS.

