Daridorexant (ACT-541468) Insomnia and comorbid nocturia Protocol ID-078A401 Version 3

4 September 2023, page 44/122

Objectives	Endpoints in period I and period II			
	• Changes from baseline to Week 1, Week 2, Week 3, and Week 4 in Patient Global Impression of Change (daytime and nighttime symptoms)			
	 Change from baseline to Week 4 in Patient Global Assessment of Disease Severity (daily life) Change from baseline to Week 4 in Patient Global Impression of Change (daily life) 			
	• Change from baseline to Week 2 and Week 4 in EQ-5D-3L score			
	• Treatment satisfaction at Week 4 assessed via NRS			
	• Treatment period preference at Visit 8 (EOTP II)			
To explore a) the sensitivity of the IDSIQ to detect clinical changes in this study population and b) the use of narratives to report subject's perception of treatment effect	 The change from baseline to Week 1, Week 2, Week 3, and Week 4 in all IDSIQ domains The subjects will be asked to complete a narrative at the end of each treatment period. More details on the analysis will be provided in the SAP. 			
To assess the safety and tolerability of daridorexant	Safety endpoints			
	Safety monitoring will include:			
	• Occurrence of TEAEs up to 5 days after EOTP I and/or EOTP II.			
	• Occurrence of treatment emergent AESIs up to 5 days after EOTP I and/or EOTP II.			
	• Occurrence of treatment-emergent serious adverse events up to 5 days after EOTP I and/or EOTP II.			
	Occurrence of TEAEs leading to premature discontinuation of the study and/or treatment.			
	• Change from baseline to EOTP I and EOTP II in vital signs (systolic blood pressure, diastolic blood pressure, and pulse rate).			
	• Change from baseline to EOTP I and EOTP II in morning sleepiness as determined by the scores on the VAS in the morning.			
	• Occurrence of suicidal ideation, suicidal behavior, and/or self-injurious behavior with / without suicidal intent based on the C-SSRS [©] at Visit 1, Visit 4, Visit 5, Visit 8, and Visit 9.			

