3.5 Appropriateness of endpoints

This study is a post-approval study and aims to investigate the effect of daridorexant on managing insomnia as well as frequent nocturnal voids (nocturia). The chosen endpoints in this study have not been adequately statistically powered except for sTST, however it is anticipated that the study is large enough to detect efficacy and safety signals of daridorexant on nocturia and sleep variables.

This study will assess sleep-related endpoints such as sTST, which has been selected as a primary endpoint as it is a clinically meaningful subjective endpoint that has already showed good response during the first weeks of treatment in both pivotal Phase 3 studies of daridorexant, although in a different subject population (insomniacs diagnosed through DSM-5 criteria, without nocturia). By measuring an improvement in sTST, the study will capture the effect of daridorexant on both wake periods at the beginning and end of the night. Nocturia by definition causes disruption of sleep continuity, and the need to void occurs throughout the entire night; in fact, the number of voidings has been significantly associated with the number of hours of sleep per night [Coyne 2003]. Moreover, these subjects have been diagnosed with insomnia and will likely experience sleep problems throughout the full night. Therefore, sTST is the variable that correlates best with both conditions.

Furthermore, to assess the potential effects of daridorexant on nocturia, this study will also measure nocturia-related variables such as the number and volume of voidings, as well as the nocturia quality of life questionnaire. As even ≥ 2 voidings during the night are considered clinically meaningful [Kim 2016], it is expected that a reduction in the number of voidings will directly result in a clinical benefit in these subjects. Additionally, with the nocturia quality of life questionnaire, the change in nocturia symptoms can be quantified into an impact on the subject's life.

Finally, this study will also assess the sensitivity to change of the IDSIQ, thus providing further information on the applicability of this instrument in the population in this study.

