9.2.4 Analysis of other efficacy endpoints

The analyses of all other exploratory efficacy outcomes will be described in detail in the SAP. Exploratory variables may also be analyzed by subgroup. Exploratory efficacy endpoints will be analyzed at each relevant time point listed in the schedule of activities [Table 1] along with any data from unscheduled visits as appropriate.

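### The exploratory objective on the IDSIQ's sensitivity to clinical change has no analysis that addresses it: the SAP plans by-treatment summaries and a treatment contrast, and never relates IDSIQ change to the weekly PGA-S and PGI-C ratings

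*SAP*

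**What the plan says.** Protocol section 3.1 lists among its exploratory aims "the sensitivity of the IDSIQ to detect clinical changes in this study population". Section 3.5 repeats the intent ("this study will also assess the sensitivity to change of the IDSIQ") and gives the reason: to learn whether the instrument is applicable in this population. The synopsis has the same item.

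Table 3 in protocol section 3.4 gives this aim its own row, shared with the narratives, and maps it to "The change from baseline to Week 1, Week 2, Week 3, and Week 4 in all IDSIQ domains". Protocol section 9.2.4 leaves the method to the SAP: "The analyses of all other exploratory efficacy outcomes will be described in detail in the SAP".

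The SAP then provides the following:

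- Section 3 (objectives) does not mention the aim.
- Section 6.3.3.5.2 plans weekly averages and changes summarised by treatment, and then: "Changes from baseline to Week 1–Week 4 will also be analyzed for all IDSIQ scores based on an MMRM". The model is that of section 6.1.3, with treatment, period, week, treatment by week and baseline as terms. Its target is the daridorexant-placebo difference.
- Sections 6.3.3.4.3 and 6.3.3.4.6 summarise PGA-S and PGI-C on their own.
- Section 7.7 sends the narratives, and nothing else, to a separate plan.
- Section 11.4 lists the MMRM as the only added IDSIQ analysis.

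**The concern.** Sensitivity to change is a property of the questionnaire: do its scores move when the subject's condition moves? A treatment difference answers another question, namely whether the drug moved the scores. The two coincide only if the drug's effect on daytime symptoms in this population is already known.

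If the IDSIQ difference is near zero, the planned output cannot separate an insensitive instrument from a drug without daytime benefit here. If it is clearly positive, the score responded on average, but nothing shows that individual score changes follow what subjects themselves report. Either way, the study report would hold no estimate of responsiveness, although the study collects a subject rating of the same concept on the same weekly rhythm.

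**Working it through.** The documents give no figure for this objective, so there is none to reproduce. Protocol section 3.5 says that only sTST is adequately powered.

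**1. What the planned contrast can distinguish.** Take a two-sided paired t-test at 0.05 with n = 50 and an assumed standardised IDSIQ treatment effect of 0.4. The noncentrality is 0.4 × √50 = 2.83 on 49 degrees of freedom, which gives 79% power. Only the mean and SD of the IDSIQ difference enter. In a simulated check, the correlation between the IDSIQ difference and the anchor difference was set to 0, 0.3 and 0.6. The mean stayed at 0.40 and the SD at 1.00, so power was 79% in all three cases. With no drug effect, the rejection rate is 5% even for a fully responsive instrument. The contrast carries no information on whether scores track the subject's own rating.

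**2. Whether usable anchors exist** (protocol 3.2.2, 3.2.4, 3.2.5; SAP 6.3.3.4.2, 6.3.3.4.5, 6.3.3.5.1).

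| | IDSIQ | PGA-S / PGI-C (daytime symptoms) |
|---|---|---|
| Period covered | mean of daily scores over 7 days | 7-day recall |
| Planned days | 2–8, 9–15, 16–22, 23–29 | 8, 15, 22, 29 |
| Accepted days | as above | 6–10, 13–17, 20–24, 25–36 |
| Baseline | 7 days before Visit 2 | PGA-S at Visit 1; PGI-C refers to the week before treatment started |

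As planned, each anchor falls on the last day of an IDSIQ window. Three mismatches remain:

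- **Baseline.** Screening lasts 14–21 days, so the PGA-S baseline week ends at least 14 days before Visit 2. The IDSIQ baseline starts 7 days before Visit 2. The two do not overlap.
- **Week 4.** An accepted anchor can fall 36 − 29 = 7 days after the IDSIQ window closes, possibly in washout.
- **PGI-C in Period II.** Its reference week could be the one before Period I or the one before Period II.

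**3. A comparison that avoids the baseline mismatch.** Each measure has one pre-treatment baseline B that serves both periods. For either measure, (Week 4 in Period II − B) − (Week 4 in Period I − B) = Week 4 in Period II − Week 4 in Period I. The baseline cancels, and each subject gives one independent pair. Higher scores mean worse on both scales, so a responsive instrument should show a positive correlation.

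**4. Precision.** Use the Fisher z interval: z = atanh(r), half-width 1.96/√(n − 3) = 1.96/√47 = 0.286 for n = 50, then back-transform. Power to show r > 0 is Φ(z√47 − 1.96). The r values are assumptions, because the documents give none.

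| Assumed r | z | z limits | 95% CI for r | Power for r > 0 |
|---|---|---|---|---|
| 0.3 | 0.310 | 0.024, 0.595 | 0.02 to 0.53 | 56% |
| 0.4 | 0.424 | 0.138, 0.710 | 0.14 to 0.61 | 83% |
| 0.5 | 0.549 | 0.263, 0.835 | 0.26 to 0.68 | 96% |

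The plan expects less than 3% dropout. With 48 pairs the first two intervals become 0.02 to 0.54 and 0.13 to 0.61.

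**The case against.** The SAP carries out the protocol's own mapping: Table 3 assigns IDSIQ change from baseline to this aim, and the SAP analyses exactly that. Protocol sections 2.3 and 6.1.3 report that 50 mg improved daytime functioning in insomnia, so a visible IDSIQ difference would be some evidence that the scale can move. Psychometric validation was done in ID-078A203 (protocol 3.2.2). Preferring an anchor-based method is partly a choice of method.

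This stands as far as it goes: a treatment difference is indirect evidence. It does not close the gap. Protocol section 2.4.1 calls efficacy in this population unknown, section 3.5 says the Phase 3 subjects had no nocturia, and the aim as worded concerns the instrument in this population. The objection about anchor quality also stands. SAP section 11.3 acknowledges problems with the weekly PGA and PGI data collection, and the mismatches shown above are real.

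A reader might infer several stronger things that the documents do not support:

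- **That the trial cannot answer the question.** It is the written analysis that does not; the data permit one.
- **That the treatment difference is the only IDSIQ output.** By-treatment summaries are also planned, and mean and SD are default statistics (SAP 8.1). A standardised response mean by treatment could be worked out from them, though none is planned and it would not be split by anchor.
- **That the aim is a formal test, or would be declared met.** The protocol says explore and assess, and sets no success criterion.
- **That existing data suffice to separate useful from absent responsiveness.** No threshold for useful is defined, and at r = 0.3 the interval barely excludes zero.

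**Conclusion.** The point holds in a limited form. The protocol states an instrument-level exploratory aim, and no planned analysis relates IDSIQ change to an independent measure of change, so the plan as written yields no estimate of responsiveness. The primary estimand, the safety analyses and the treatment-effect conclusions do not depend on it.

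A responsiveness analysis is feasible with modest precision. The intervals above rest on 50 independent pairs, assumed correlations and an approximately normal scale. PGA-S (daytime symptoms) is a single 6-point item, so the intervals are approximate, and poorly aligned or missing anchors would widen them. They do not apply to a pooled analysis that uses two periods per subject without allowing for the repetition. The weight is that of an optional, low-cost improvement to an exploratory objective.

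**What to change.** Before unblinding, add an exploratory responsiveness analysis to SAP section 6.3.3.5.2. If unblinding has already happened, label it post hoc.

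- **(a) Main.** Correlate, across subjects, the Period II minus Period I difference in Week 4 IDSIQ (total and domains) with the same difference in PGA-S (daytime symptoms), with 95% CIs. The drug shifts the two sequences in opposite directions, so also show the result adjusted for sequence.
- **(b) Supportive.** Show IDSIQ change by PGI-C (daytime symptoms) category and against PGA-S change, pooled over treatments in a model that allows for repeated measures within subject. State the PGA-S/IDSIQ baseline mismatch as a limit.
- **(c)** Give standardised response means in improved and in unchanged subjects, where cell sizes allow.

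Use only anchor entries that align with the IDSIQ weekly window. For Week 4, exclude or flag late entries within Days 25–36. Treat PGI-C in Period II as a sensitivity analysis. Report the IDSIQ MMRM as an efficacy result.

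The alternative is to reword the objective as the treatment effect on the IDSIQ, which the present plan already answers.

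The first option costs a paragraph and a few tables from data already collected, with no added burden on subjects. The second costs a change of wording.

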# 6.3.3.6 Treatment satisfaction

The Numeric Rating Scale collects information regarding treatment satisfaction during the clinical trial by asking the subjects to mark the number that best describes overall satisfaction on a scale from 0 ('Not at all satisfied') to 10 ('Extremely satisfied). Self-reported treatment satisfaction is assessed on the morning of Visit 4 and Visit 8 on the eDiary.

A paired t-test will be applied to the within-subject differences (daridorexant 50 mg vs placebo) to test for differences between the two treatments. The output will contain the mean estimate (including 95% CI) and the associated p-value.

Treatment satisfaction will be summarized descriptively by treatment.

